### **Phase I. Open trial and RCT**

**Study overview.** In this treatment development grant, 70 adolescents in Probation will be recruited to participate in the study. The first 10 will participate in an iterative development open trial. Then 60 youth will be randomized to: 1) the screening/brief intervention safety planning intervention, or 2) standard practice.

**Open Trial Design.** A total of 10 youth will be recruited for open trial in order to: a) test the protocol's applicability in Probation, and b) train the mental health counselors in the protocol. We have used this 2 phase approach extensively in prior studies. The open trial will occur in months 5 - 8 after counselor training. The protocol and procedures will be modified as necessary after the first 5 participants and then again after 10 pilots have been run through the protocol and prior to conducting the pilot RCT

[figure not shown]
**Overview of RCT Trial Procedures.** When youth arrive for their first Probation appointment, they are asked to complete the MAYSI/NSSI assessment. Youth who flag in on the MAYSI or NSSI item on this first screen, will be referred by their PO to the mental health counselor who will approach them about participation in the study. If the parent/caregiver consents to the study, the mental health counselor will then meet with the youth, physically separate from the parent/caregiver, to describe study procedures in detail (**including the fact that only youth who are positive on the secondary screen continue in the study**) and obtain juvenile assent without parental presence (see **Human Subjects**). Consenting procedures will also include permission to access court records. All youth will then complete the complete the Self-Injurious Thoughts and Behaviors Interview 2.0 (SITBI-Short Form^91, see below), to more thoroughly assess self-injurious behavior. Families will then be referred back to their PO to complete the secondary screen. If the youth screens in, he/she is then randomized to either standard practice or the safety planning intervention.

Follow-up assessments will also be completed at 1- and 3-months post-baseline to gather data on youth outcomes related to treatment, self-harm, and recidivism. No juvenile will ever be sanctioned by the court for not agreeing or being unable to participate in the research study (see **Human Subjects/Letter of Support**).

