representation will be about 22% Africa American or Black (and other) and 72% White. **Estimated Sample Size and Retention Rates.** In 2016, the RIFC handled offenses for 2,634 juveniles of whom 764 (29%) were female and 2,581 (98%) who were in the 12-17 year old age range. The Juvenile Intake Department, for example, screens more than 904 juveniles per year and, of those youth who are screened, approximately 10% (N=89) flag for recent SI. In 2015, the detention center admitted 470 youth. *Probation had a caseload of 375 in 2015. Of these youth, it is estimated that 20% of youth screen positive for current risk of self-injurious behavior (N=75). Even with a conservative acceptance rate of 60%, we would be able to recruit about 45 youth per year and meet our 20 month projected enrollment goal of 60 participants, i.e. about 3 per month (3 x 20 = 60). Using a conservative follow-up rate of 80% (see **Retention**) of the 60 enrolled and retained participants, approximately 48 are expected to complete the 3-month follow-up.* This approach is feasible given our excellent working relationship with the JJS, including the RIFC, and prior experience recruiting from the juvenile intake department (see RIFC Chief Judge and Probation Letters of Support). MPI [name] collaborated on a 24-month longitudinal epidemiological study of first-time CINI offenders at the RIFC and we successfully recruited the entire sample of 400 first-time offending CINI youth (DA034538). MPI [name] is also currently recruiting at the RIFC juvenile intake department for a baseline sample of suicidal CINI youth for her NIMH K23 Mentored Career Award. MPI [name] also successfully established a referral system from RIFC to his NIAAA (AA017659) and NIDA (DA0029871) trials for youth with substance use-related court involvement.

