### **Phase I: Data Analysis Plan**

Prior to conducting analyses for the project aims, a series of routine procedures will be conducted to ensure the data accuracy/adequacy. All forms will be checked for missing data and all data will be double entered and backed-up daily. Descriptive statistics will be examined for distributional properties of the variables (e.g., normality, internal consistency). The data will be transformed to achieve normality if needed.

We will conduct analyses in an intent-to-treat (as randomized) manner, and examine as primary analyses unadjusted and secondarily adjusted for selected covariates identified above. Masking integrity will be reviewed. ANCOVA (outcome regressed on baseline) methods will be used, and linear mixed effect models will be used to account for non-independence of repeatedly observed outcomes.

We will examine attrition by comparing follow-up assessment completers and non-completers on socio-demographic and baseline data to determine if they differ systematically. Consistent with an intent-to-treat model, we will include all randomized participants in the analyses. Attrition/Missing Data. It is anticipated that less than 20% of subjects will not have follow-up data. We will test for differential attrition across the experimental condition and the baseline comparison. The analyses described below can account for attrition at the follow-up points. We will employ multiple imputation as our primary approach to missing data [138] and will conduct a sensitivity analysis treating all participants lost to follow-up as treatment failures at the point of loss, i.e. assuming no change on their self-injury-related mechanisms or outcomes. If our primary conclusions are similar with and without extreme missing data assumptions, confidence in the findings will be higher.

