We will use generalized linear mixed models to test hypotheses that participants randomized to the safety plan condition will have significantly improved outcomes compared with those who receive standard practice. This approach accommodates varying numbers of observations across individuals (allowing the inclusion of all randomized participants) while controlling for within-subject correlation. Scores from continuous measures are the dependent variables and treatment condition is the primary independent variable. Analyses will also be conducted co-varying baseline SITBI scores. These hypotheses will be evaluated by regressing the outcome variables as observed on the 1 and 3-month follow-ups on treatment condition, and a time by treatment condition interaction in a general linear mixed effect modeling framework. Main inferences will be based on post-hoc omnibus tests of treatment group effects pooled over time points, and secondary inferences will be drawn from the time-specific outcomes.

The current study also seeks to illuminate factors that may better guide treatment decision making by identifying those who are most likely to benefit from the proposed interventions. Specifically, in exploratory analyses, we will examine sex, race, and ethnicity to address the barrier of racial disparities.

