**Power:** We will recruit 70 participants in the RCT which should be sufficient to make judgments regarding feasibility and acceptability. We do not have pilot data available for calculating effect sizes to present here because R34 applications do not require pilot data but are used to collect pilot data regarding feasibility and acceptability. Two-way comparisons across treatment groups result in 80% power to detect effect sizes amounting to standardized mean differences (Cohen's d) of 1.0 or higher as statistically significant under a two-sample t-test analytic framework. With repeated measures for outcomes, under assumptions of reasonable reliability for the outcomes ( $r = .8$ ) and high autocorrelation for repeated measures ( $r = .64$ ), we will be able to detect smaller differences ( $d = .62$ ) in pairwise comparisons (where  $.62 = (16*(1-.8^2)/15)^{0.5}$ , following Lehr [137]). A medium ES when power is set at .8, is typically considered a clinically relevant finding. Thus, if high levels of feasibility and acceptability are found, this would suggest that the protocol should be tested in a larger trial. For power of .8 and a clinically relevant ES, i.e., a medium ES ( $d = .5$ ), a sample of 64 per group would be required in a future R01.

**Aim 2: Service level mechanisms** will be examined as potential mediators of intervention effects. Success of treatment linkage, including barriers to outpatient treatment, and the equity of intervention fidelity and treatment linkage across sex, race, and ethnicity will be compared following the analytic approach summarized in Aim 1.

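### The follow-up-only mixed model does not by itself include all randomized youth, and the plan neither says it is fitted to the imputed data nor uses baseline SITBI in its primary analysis

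*Combined protocol and SAP*

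**What the plan says.** All the relevant analysis text is in the Phase I: Data Analysis Plan.

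- **Attrition/Missing Data.** The analysis is intent-to-treat and every randomized participant is to be included. "We will employ multiple imputation as our primary approach to missing data", with a sensitivity analysis that counts those lost as failures, that is, as showing no change. The same paragraph says the later analyses can account for attrition, and expects limited loss: "It is anticipated that less than 20% of subjects will not have follow-up data".
- **Adjustment.** Unadjusted analyses are primary and covariate-adjusted ones secondary. ANCOVA on baseline is also mentioned.
- **Mixed models.** The reason given for choosing them is: "This approach accommodates varying numbers of observations across individuals (allowing the inclusion of all randomized participants) while controlling for within-subject correlation". The hypotheses are then tested by "regressing the outcome variables as observed on the 1 and 3-month follow-ups on treatment condition" and a time-by-treatment term. Analyses with baseline SITBI as a covariate are listed as additional.
- **Numbers.** In Phase I. Open trial and RCT: "Then 60 youth will be randomized to: 1) the screening/brief intervention safety planning intervention, or 2) standard practice". Retention is planned at 80%, so "approximately 48 are expected to complete the 3-month follow-up".

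No section says whether the mixed model is fitted to the observed or to the imputed data, or which variables enter the imputation model.

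**The concern.** A mixed model tolerates a missing visit only when the participant contributes at least one other response. Here baseline is not a response. A youth seen at 1 month but not at 3 months stays in; a youth seen at neither has no row and leaves the analysis. The property claimed for the model is therefore untrue of that model fitted to observed data.

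Imputation would restore the missing youth, but the text gives two separate reasons for full inclusion and does not connect them. Two analysts could each follow the plan and report different sample sizes and different estimates.

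The analysis named as primary is the exposed one. Without baseline SITBI in the model or in an imputation step, nothing corrects for loss that follows baseline severity in one arm more than in the other. The plan itself treats this as possible, since it will compare completers with non-completers on baseline data and test for differential attrition.

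**Working it through.** **1. The plan's own figure.** 60 × 0.80 = 48, as stated. Twenty per cent of 60 is 12, so an expectation of less than 20% without follow-up means fewer than 12 youth. (The Power paragraph puts 70 in the RCT; Phase I. Open trial and RCT shows 70 = 10 open-trial + 60 randomized, so 60 is used here.)

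**2. Who enters the model.** A mixed model of 1- and 3-month values on arm, time and their interaction, with a random intercept, was fitted to 60 simulated youth. In that draw 14 had no follow-up and the fit used 60 − 14 = 46.

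**3. Size of the possible bias.** From the plan: 60 randomized and a correlation of .64 (the autocorrelation in the Power paragraph). Assumed: 30 per arm, the .64 applies to every pair of visits including baseline, unit SD, no true effect, both follow-ups lost together, loss random in one arm, and log-odds of loss in the other arm rising by s per baseline SD (s = .5, 1, 2). The slopes and the one-arm mechanism are not in the documents.

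- Baseline shift among retained youth in the affected arm: shift = ∫ z φ(z)[1 − expit(a + sz)] dz / (1 − p), with a set so that the loss rate is p.
- Bias of the unadjusted comparison = .64 × shift.
- Variance of the mean of two follow-ups = (1 + .64)/2 = .82.
- Unadjusted SE at 20% loss (24 per arm) = √(2/24 × .82) = .261. At 6% loss (28.2 per arm) = √(2/28.2 × .82) = .241.
- Approximate false-positive rate = P(|Z + bias/SE| > 1.96).

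| Loss p | s | shift | bias (SD) | \|bias\|/SE | false positives |
|---|---|---|---|---|---|
| 20% | .5 | -.096 | -.06 | .24 | 5.6% |
| 20% | 1 | -.173 | -.11 | .42 | 7.1% |
| 20% | 2 | -.262 | -.17 | .64 | 9.8% |
| 6% | .5 | -.030 | -.02 | .08 | 5.1% |
| 6% | 1 | -.056 | -.04 | .15 | 5.3% |
| 6% | 2 | -.091 | -.06 | .24 | 5.7% |

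The 6% rows correspond to the 94% 3-month retention that Protection against Attrition reports from an earlier study. A simulation of 8,000 trials per setting gave -.061, -.110 and -.168 SD at 20% loss and -.016, -.034 and -.056 SD at 6%.

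**4. When there is no bias.** In a large-sample run with 20% loss, the unadjusted estimate was about 0 (within .003) both when loss was random and when it rose with baseline equally in the two arms (log-odds .7 per SD).

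**5. With baseline used.** The residual variance of the mean follow-up given baseline is .82 − .64² = .4104, so the SE at 20% loss is √(2/24 × .4104) = .185; simulated values were about .19. Simulated bias was within .003 SD and false positives were about 5% throughout. Imputation by regression on baseline within arm also gave a bias of about 0 when loss ran in opposite directions by arm (log-odds .35, .7 and 1.0 per SD), where the unadjusted estimate was off by -.09, -.17 and -.22 SD.

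**The case against.** The strongest reply is that imputation and a mixed model are not rivals: one handles missing data, the other analyses the result. Since imputation is named as primary, the mixed model can be read as fitted to imputed data, and then all 60 enter. The phrase about values as observed may only name the time points. This stands as far as it goes. A reader might infer that the analysis set is simply wrong, or that the trial's intent-to-treat analysis is really one of youth with any visit. The documents do not support that; it follows only if the model is run on observed data, which the plan leaves open.

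The plan also already contains baseline-adjusted analyses, ANCOVA, attrition comparisons and a no-change sensitivity analysis. These would help to reveal or correct the bias. But the adjusted analyses are secondary, and the primary one remains unadjusted.

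Twelve of 60 is a ceiling. The 80% figure is for 3-month completion, and a youth seen only at 1 month stays in the model. That stands, and it is why the 6% rows are shown.

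Two further inferences fail. One is that imputation and the follow-up-only model agree only if nothing predicts loss: they also agree on average when loss depends on baseline equally in both arms. The other is that the SDs and pre-post correlations sought under Primary Aim would be lost. The plan does not say they come from this model, and descriptive statistics or ANCOVA can supply them.

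**Conclusion.** The point holds in limited form. The stated reason for full inclusion is incorrect for a model of follow-up values fitted to observed data, and the plan does not link that model to the imputation that would make inclusion true. Fewer than 12 of 60 youth are affected on the plan's expectation.

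Any bias needs three things together: a fit to observed data, no baseline term, and loss that depends on baseline severity differently by arm. The largest figure, -.17 SD with about 10% false positives, needs 20% total loss and a slope of 2 in one arm only. At 6% loss the same slope gives about 6% false positives. These are illustrations under assumed mechanisms, not forecasts.

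The lower standard error with baseline in the model does not depend on differential loss. It does depend on the .64 correlation holding between baseline and follow-up.

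Primary Aim makes feasibility and acceptability the main question and disclaims estimating an effect size. The consequence is therefore modest, but the plan still specifies hypothesis tests, and the correction is cheap.

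**What to change.** For continuous SITBI scores, make the main model use baseline in one of two ways:

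1. Treat baseline, 1-month and 3-month scores all as responses, with a common baseline mean, unstructured covariance and treatment effects at 1 and 3 months. Every youth with a baseline SITBI then enters.
2. Keep the follow-up model, add baseline SITBI as a covariate, and state that it is fitted to the multiply imputed datasets, with baseline SITBI and arm in the imputation model.

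Either is acceptable. For outcomes that are not continuous, such as attempts or NSSI analysed as events or counts, use the imputation route.

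Delete the statement that the mixed model alone includes all randomized youth. If an observed-data fit is kept as a supporting analysis, say that youth with no follow-up are left out of it and report how many.

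The cost is a few sentences of plan text and a small code change. No new data are needed, since the SITBI is already collected at baseline. Both routes assume data are missing at random given baseline and arm (and any follow-up observed); the planned no-change sensitivity analysis should stay.

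### The outcome model lists treatment and time-by-treatment but no main effect of time; under 0/1 product coding, which the plan does not rule out, this distorts the secondary 1- and 3-month effects

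*Combined protocol and SAP*

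**What the plan says.** The mixed-model paragraph of the Phase I Data Analysis Plan describes the analysis as "regressing the outcome variables as observed on the 1 and 3-month follow-ups" and then names the predictors: "on treatment condition, and a time by treatment condition interaction in a general linear mixed effect modeling framework". Two inferences are drawn. For the first, "Main inferences will be based on post-hoc omnibus tests of treatment group effects pooled over time points". For the second, "secondary inferences will be drawn from the time-specific outcomes".

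Nothing else in the document completes the list of terms:

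- The opening of the same section says only that ANCOVA will be used and that "linear mixed effect models will be used to account for non-independence of repeatedly observed outcomes". It gives no fixed effects.
- The baseline-adjusted version ("Analyses will also be conducted co-varying baseline SITBI scores") adds a covariate that is constant within a participant, so it cannot stand in for a time effect.
- No section says whether treatment or time is entered as a number or as a factor, or how either is coded.

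**The concern.** A model with an interaction normally carries both lower-order terms. Here one of them, time, is absent. If treatment is a 0/1 indicator and the interaction is the product of that indicator with time, every time term is zero in the standard-practice arm. The model then has one mean for that arm at both visits. The experimental arm keeps a free mean at each visit. If both arms change by the same amount between 1 and 3 months, the model can show that change in the experimental arm only, and it enters the visit-specific treatment contrasts.

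At stake are the visit-specific results for suicidal ideation and for attempts/NSSI, which the Primary Aim text names as the main clinical outcomes. With a common decline and no treatment effect, the analysis would tend to show an apparent harm at 1 month and an apparent benefit at 3 months. Either could colour the design of the next trial.

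**Working it through.** **The plan's own figure.** The only figure tied to the repeated-measures analysis is the detectable difference in the Power paragraph: sqrt(16 x (1 - 0.8^2)/15) = sqrt(0.384) = 0.62. It reproduces, and this point does not dispute it.

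**Inputs.**

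- Two outcome visits, 1 and 3 months (Data Analysis Plan).
- Correlation between repeated measures 0.64 (Power paragraph).
- Randomized: 60 ("Then 60 youth will be randomized to: 1) the screening/brief intervention safety planning intervention, or 2) standard practice"). Completers: "approximately 48 are expected to complete the 3-month follow-up". The allocation ratio is not stated. With 1:1 assumed, this is 30 randomized and 24 completers per arm.
- Assumed, because the documents give no figure: a common change c from 1 to 3 months of -0.2, -0.3 or -0.5 SD, unit SD at each visit, no true treatment effect, and two-sided 5% tests.

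**Step 1: bias under 0/1 product coding, complete data.** Set the true means to 0 at 1 month and c at 3 months in both arms. The standard-practice arm is fitted by one mean, which is the average of its two visits, c/2. The experimental arm is fitted exactly at 0 and c.

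- 1-month contrast: 0 - c/2 = -c/2
- 3-month contrast: c - c/2 = +c/2
- Pooled contrast: (-c/2 + c/2)/2 = 0
- Product term: c

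**Step 2: rejection rates, 24 per arm, normal approximation.** The variance of a visit-specific contrast is 1/24 for the experimental arm plus ((1 + 0.64)/2)/24 = 0.82/24 for the single standard-practice mean. The standard error is sqrt(1.82/24) = 0.275. The product term is the experimental arm's within-person change, with standard error sqrt(2 x (1 - 0.64)/24) = 0.173. Rejection is P(Z > 1.96 - bias/SE) + P(Z < -1.96 - bias/SE).

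| Common decline (SD) | False contrast, size (SD) | Bias/SE | Time-specific rejection | Product-term bias/SE | Product-term rejection |
|---|---|---|---|---|---|
| 0.2 | 0.10 | 0.36 | 6.5% | 1.15 | 21% |
| 0.3 | 0.15 | 0.54 | 8.5% | 1.73 | 41% |
| 0.5 | 0.25 | 0.91 | 14.8% | 2.89 | 82% |

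Random-intercept models fitted to 400 simulated trials with a 0.5 SD decline agree. With 24 per arm, rejection was 17.8% at 1 month, 14.0% at 3 months, 78.0% for the product term and 5.8% for the pooled effect. With 30 per arm it was 17.5%, 19.0%, 86.5% and 6.0%.

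**Step 3: other codings.** With treatment coded +/-0.5, the 1-month, 3-month and pooled contrasts are all 0 for the same c. With treatment and time both entered as factors, treatment plus treatment-by-time has rank 4, the same as the full factorial on four cell means. The visit-specific contrasts are then unbiased.

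**Step 4: pooled effect with missing visits, 0/1 coding, no imputation.** Take 30 per arm with 6 in each arm (20%) missing at 3 months at random. In the standard-practice arm, the 24 complete pairs carry weight 24 x 2/1.64 = 29.27 around c/2, and the 6 single visits carry weight 6 around 0. At c = -0.5 the fitted mean is 29.27 x (-0.25)/35.27 = -0.207. The pooled contrast becomes -0.25 + 0.207 = -0.04 SD, and the 3-month contrast -0.5 + 0.207 = -0.29 SD.

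**Step 5: with the time term added.** At c = -0.5 with 30 per arm, the mean contrasts were +0.01 SD at both visits. Rejection was 5.2% (1 month), 5.2% (3 months), 5.0% (pooled) and 6.2% (interaction), with simulation error of about one percentage point.

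**The case against.** The strongest reply is that the bias needs a coding that the plan never states. Visit-specific and pooled contrasts over two discrete visits fit a factor parameterisation at least as well as a product term, and under that reading the visit-specific estimates equal those of the full model. Naming only the interaction may also be shorthand. This stands: the bias is a risk of the wording, not a certain result. It does not make the wording adequate, because the answer should not depend on an unstated coding choice. Factor coding also leaves the term labelled as the interaction with a different meaning, since it then tests any change over time within either arm.

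A reader might infer from the 21%, 41% and 82% rejection rates that the trial's error control is badly broken. The documents do not support that. Those rates belong to the product term, and the plan names no inference from it. The time-specific tests, which the plan does use, are inflated far less.

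A reader might also infer that the main inference is compromised. With complete data it is not, under any coding tried. Missing 3-month visits shift it slightly (Step 4), but the plan makes multiple imputation its primary approach to missing data. Imputed data sets have both visits for everyone, which is the balanced case.

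Finally, the size of c is unknown. Entry after a positive screen argues for change from baseline, but only change between the two follow-ups matters here. The plan itself calls the 3-month follow-up a high-risk period, so a decline within it is plausible but not established.

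**Conclusion.** Wrong as written, low severity. The listed fixed effects omit time, and no other section supplies it. Under 0/1 product coding the false time-specific contrasts are half the common change, with opposite signs at the two visits. For the assumed declines of 0.2 to 0.5 SD that is 0.10 to 0.25 SD, with error rates of about 6% to 15% in place of 5%. Under +/-0.5 or factor coding these contrasts are unbiased. The pooled main test keeps about 5% error. At c = -0.5 SD its estimate moves by about -0.04 SD if 20% are missing at 3 months and nothing is imputed.

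These sizes rest on 1:1 allocation, correlation 0.64, two-sided 5% tests and an assumed range for c. The reach is limited to secondary results. The primary aim is feasibility and acceptability, and the plan says that it does not seek a preliminary effect size.

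**What to change.** State the fixed effects as treatment, time (categorical: 1 and 3 months) and treatment x time, with a random intercept for participant. Include the baseline value in the baseline-adjusted analysis. Define the pooled effect and the 1- and 3-month effects as contrasts from that one model. With all lower-order terms present, these contrasts no longer depend on the coding.

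The cost is one model term and one degree of freedom. No sample size or power figure changes. If the omission is only a drafting slip, the correction is to add time to the list.
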